8.2.3 Electrocardiograms

- Triplicate 12-lead ECG will be obtained as outlined in the SoA ([Table 1](#)) using an ECG machine supplied by the Central ECG Laboratory that automatically calculates the heart rate and measures PR, QRS, QT, and QTc intervals. Refer to [Section 7.2](#) for QTc withdrawal criteria and any additional QTc readings that may be necessary.
- Three individual ECG tracings should be obtained as closely as possible in succession, and completed in less than 4 minutes.
- The ECG tracing should clearly identify the patient, include the date and time of the assessment, and include the signature and date of the person who made the local interpretation; the tracing will be archived at the study site and electronic files sent to the Central ECG Laboratory. Abnormal, clinically significant ECG results will be recorded as AEs (see [Section 8.3](#)). If there is noise or other artifacts, they will be repeated. The QTcF intervals should be reviewed based on the automatic read from the ECG machine in real time.
- All ECGs will be transferred and read centrally by a qualified vendor. The ECGs collected at the Baseline visit (prior to randomization) should be assessed locally by the Investigator for confirmation of eligibility, but the final centrally read report will serve as the document of record in the patient's source chart and from the primary ECG database (EXPERT) for the study.

- Triplicate 12-lead ECGs will be performed at least 30 seconds apart, in a supine position, resting for at least 10 minutes (without external stimulation, e.g., talking, TV, noise) and submitted for central reading. Screening ECGs will be collected prior vital signs and blood samples. On Day 1 and 8, ECGs will be taken predose and 2 hours postdose. Patients not fasting on Day 1 and 8 will have an additional 4 hr postdose ECG. On Days 15, 29, 43, 57, and 85 ECGs will be performed as the last assessment in the clinic.

8.2.4 Clinical Safety Laboratory Assessments

See [Appendix 3](#) for the list of clinical laboratory tests to be performed and the SoA ([Table 1](#)) for the timing and frequency.

The Investigator must review the laboratory report, document this review, and record any clinically relevant changes occurring during the study in the AE Section of the eCRF. The laboratory reports must be filed with the source documents. Clinically significant abnormal laboratory findings are those that are not associated with the underlying disease, unless judged by the Investigator to be more severe than expected for the patient's condition.

See [Section 7.0](#) for discontinuation criteria based on abnormal liver function tests, neutrophil values, CK values, or positive SARS-CoV-2 test.

All laboratory tests with values considered clinically significantly abnormal during participation in the study or within 30 days (+7 days) after the last dose of study treatment should be repeated until the values return to normal or Baseline or are no longer considered clinically significant by the Investigator or Medical Monitor.

- If such values do not return to normal/Baseline within a period of time judged reasonable by the Investigator, the etiology should be identified and the Medical Monitor notified.
- All protocol-required laboratory assessments, as defined in [Appendix 3](#), must be conducted in accordance with the Laboratory Manual and the SoA ([Table 1](#)).
- If laboratory values from non-protocol specified laboratory assessments performed at the institution's local laboratory require a change in patient management or are considered clinically significant by the Investigator (eg, SAE or AE), then the results must be recorded in the eCRF.
- Serum potassium levels < 3.8 mmol/L will be treated and repeated as will serum magnesium levels < LLN.

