- h. Serious AE reporting will start at the time of consent. Any AE that occurs between the time of consent and prior to dosing on Day 1 will be recorded as medical history. Treatment-emergent AEs will be collected following the first dose of study treatment on Day 1 through the Follow-up Visit (30 days after the last administration of study treatment) ([Section 5.5](#)).
- i. Unscheduled visits are allowed, as deemed necessary by the Investigator, in the event that assessments need to be repeated (eg, lab draws), safety follow-up needs to be conducted, or additional dispensing activities need to occur.
- j. Patient should be fasted for visits on Days 1 and 8, defined as 8 hours since last food. A snack is permitted 2 hours after the morning dose.

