### **3.3.9. Presentations by Study Visit**

Scheduled and unscheduled assessments collected from Visit 1 through Visit 8 for all efficacy assessments and safety assessments (labs, vital signs, and ECG) will be assigned to an analysis visit window using the study day ranges described in [Table 1](#) and [Table 2](#). All study days up to and

---

including Day 1 are in the baseline-eligible analysis visit window. The last non-missing assessment in the baseline-eligible analysis visit window will be used in any summaries that present the baseline results with the exception of ECG interpretation where the best result from the triplicate values will be chosen. Day 1 post-dose ECG, PK and vital signs assessments will be analyzed as collected. Day 8 ECG assessments, Day 8 and 85 PK assessments, and Day 8, 15, 29, 43, 57 and 85 vital sign assessments will be windowed per Table 2, then each time point will be analyzed as collected. For all other assessments, for post-baseline analysis windows, if multiple assessments occur within a given analysis visit window, the result closest to the target study day, regardless of whether scheduled or unscheduled, will be used for summary presentations. If two measurements have the same distance to the target study day, the first assessment will be used in the summary presentations with the exception of ECG interpretation where the worst result from the triplicate values for the given visit and timepoint will be used. All assessments will be presented in the listings. In addition to the analysis visits indicated in Table 1 and Table 2, for patients who prematurely discontinue the study, data collected during the withdrawal visit will be used as an EOS assessment for these patients. The EOS assessment will be included in safety analyses.

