**Table 2: Visit Windows Assessments Other than DLQI**

CRF Visit	Target Study Day	Analysis Visit	Study Day Range
Visit 1	-28 to -1	Baseline	<1 or Day 1 pre-dose
Visit 2	1		
Visit 3	8	Week 1	[2 – 11]
Visit 4	15	Week 2	[12 – 21]
Visit 5	29	Week 4	[22 – 35]
Visit 6	43	Week 6	[36 – 49]
Visit 7	57	Week 8	[50 – 70]
Visit 8(EoT/ET)	85	Week 12	[71 – 98]
Visit 9(EoS)	30 days after last dose	EOS	Latest assessment after the EoT/ET

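### The SAP takes the latest post-treatment result as the EOS laboratory value, so a retest can replace a clinically significant abnormal Visit 9 result and tilt that row toward recovery

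*Protocol*

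**What the plan says.** **Retest rule (Protocol 8.2.4).** The rule covers "All laboratory tests with values considered clinically significantly abnormal" that arise "during participation in the study or within 30 days (+7 days) after the last dose of study treatment". Such tests "should be repeated until the values return to normal or Baseline or are no longer considered clinically significant by the Investigator or Medical Monitor". The period takes in the Visit 9 draw, which the Schedule of Assessments places 30 days (+7) after the last dose. The same schedule allows unscheduled visits for repeat laboratory draws.

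**Selection rule for EOS (SAP 3.3.9, Table 2).** For every assessment except DLQI, the Visit 9 row carries a target of 30 days after last dose. Where the other rows give a study-day range, this row says "Latest assessment after the EoT/ET". It sets no upper day limit and is not restricted to the scheduled draw.

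**Selection rule for other post-baseline windows (SAP 3.3.9).** When a window holds several results, "the result closest to the target study day, regardless of whether scheduled or unscheduled, will be used for summary presentations". On a tie, "the first assessment will be used in the summary presentations". The sentence that introduces windowing refers only to Visits 1 to 8. The same section makes the withdrawal visit an EOS assessment for early discontinuers.

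**Where the value is used.** SAP 5.5.2 presents laboratory values and changes by analysis visit. The table list in SAP Section 9 titles both the change tables (14.3.4.1.x) and the treatment-emergent abnormality tables (14.3.4.2.x) by analysis visit.

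**The concern.** Each rule is reasonable alone. Retesting an abnormal result is ordinary care, and taking the last value is a common convention. The difficulty is that retesting depends on the result. A patient whose Visit 9 value raises no concern has no further draw, so that value is also the latest. A patient with a clinically significant abnormal value is drawn again, and the draws stop once the value has recovered or is no longer thought significant. A latest-value rule therefore keeps the unremarkable results and replaces the significant ones.

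The EOS row is the only off-drug row in the laboratory tables. Readers will use it to judge whether abnormalities appear late or persist about 30 days after stopping. With retests substituted, recovery looks faster and more complete than it was at 30 days, and the tilt is larger in whichever arm has more significant abnormalities. Laboratory abnormalities are a secondary endpoint, so the row should show what was observed at the visit it is named for.

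**Working it through.** The documents give no figure for this point, so there is nothing to reproduce. The check traces the rules and then illustrates the arithmetic.

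**1. Three patients under the rules as written**

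| Visit 9 result | Retest under the general rule in 8.2.4? | EOS value under Table 2 | EOS value if the scheduled draw were used |
|---|---|---|---|
| Within range | No | Visit 9 | Visit 9 |
| Out of range, not clinically significant | No | Visit 9 | Visit 9 |
| Clinically significant; repeat two weeks later is normal and no further draw follows | Yes | The repeat | Visit 9 |

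Only the third patient's value changes, and it changes toward recovery. If the repeat is absent from the database, nothing changes. If retesting stopped at Baseline level or at non-significance, the replacement is milder but may still be out of range.

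**2. Illustration for the share abnormal.** Let n = 45, the planned number per arm (Protocol 1.1, Number of Patients), assuming all contribute an EOS value. Let k be the number with a clinically significant abnormal Visit 9 value. Let r be the share of those whose later retest is in the database and back in range. Both k and r are assumptions.

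- Share at the scheduled draw = k / n
- Share under the latest-value rule = k(1 − r) / n

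| k | Scheduled draw | r = 0.5 | r = 0.75 | r = 1 |
|---|---|---|---|---|
| 2 | 4.4% | 2.2% | 1.1% | 0% |
| 4 | 8.9% | 4.4% | 2.2% | 0% |
| 6 | 13.3% | 6.7% | 3.3% | 0% |

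For example, 4 × (1 − 0.5) / 45 = 2/45 = 4.4%. These percentages count only clinically significant values. The treatment-emergent table counts every shift outside the laboratory range, so its EOS row would also hold out-of-range values that no retest displaces.

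**3. Illustration for a mean.** Each replaced value moves the arm mean by (Visit 9 value − retest value) / n. With an assumed ALT of 200 U/L retested at 35 U/L, that is (200 − 35) / 45 = 3.7 U/L per patient. With 41 patients at 25 U/L and 4 such patients, the mean falls from (41 × 25 + 4 × 200) / 45 = 40.6 to (41 × 25 + 4 × 35) / 45 = 25.9 U/L.

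**4. Where the displaced value still appears.** SAP 3.3.9 keeps all assessments in the listings. Protocol 8.2.4 sends clinically relevant changes to the AE page. SAP 5.5.2 summarises maximum CTCAE grade for CK, neutrophils, ALT, AST and bilirubin, and SAP 3.3.8 counts a toxicity at any post-baseline visit. No other analyte has a worst-value table in SAP Section 9.

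**5. Would a closest-to-30-days rule be enough?** Suppose Visit 9 falls 36 days after the last dose, inside its window, and a retest of an abnormal Day 85 value falls at 27 days. The distances are 36 − 30 = 6 and 30 − 27 = 3 days, so the retest would be chosen. That rule can still select on outcome.

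**The case against.** **The SAP may not mean what the row says.** The row does carry a 30-day target, and the closest-to-target text is worded for post-baseline windows in general. If that text governed, a retest after Visit 9 would usually lose. However, the windowing sentence stops at Visit 8 and the Visit 9 row states its own rule, which already picks one value. On a plain reading the row governs. If closest-to-target was intended, the row contradicts it and still needs correcting.

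**Latest may be deliberate.** Protocol 4.4 dates a patient's end of study at the last successful contact, including follow-up of outstanding events, so EOS could mean final status. That is a legitimate quantity, but it does not match a row tied to Visit 9 and a 30-day target, or the by-visit tables in which it sits.

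**The safeguards are real.** A reader might infer that delayed toxicity vanishes from the report. The documents do not support that: the abnormal value stays in the listings, in AE reporting where relevant, and in the CTCAE table for five tests. The ALT illustration concerns one of those five, so only its EOS mean and by-visit rows are affected.

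**The effect is narrower than it first looks.** A reader might infer that every abnormal EOS value is replaced by a normal one, or that the row's abnormality rate must fall to near zero. Neither follows. The general rule says should, it is triggered only by clinically significant values, and it lets retesting stop short of the normal range. Nor is it right that retests can never enter the other windows: selection there ignores whether a draw was scheduled, so a retest nearer the target can be used.

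**Importance.** This is one off-treatment row of descriptive tables in a 90-patient Phase 2a study, and no test depends on it. That limits the weight of the point but leaves the mechanism in place.

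**Conclusion.** The point holds in limited form. Followed as written, the two rules let a retest after Visit 9 replace a clinically significant abnormal Visit 9 value in the EOS row of the by-visit laboratory change and treatment-emergent abnormality tables. The bias is toward recovery.

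This rests on three conditions: the Visit 9 row of Table 2 governs EOS, that row appears in the by-visit tables, and the later retest is in the analysis database. The size cannot be computed, because the documents give neither the frequency of significant abnormalities at Visit 9 nor the share that resolve; the figures above are illustrations on assumed inputs. Efficacy results and the other laboratory rows are not touched by the EOS rule. It is worth correcting before database lock as a safety-summary definition.

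**What to change.** In SAP Table 2, define the EOS laboratory value as the scheduled Visit 9 draw (30 days, +7, after last dose). Use an unscheduled assessment, the one closest to 30 days after last dose, only when the scheduled draw is missing. Footnote how many EOS values come from that fallback, since a retested patient is more likely to have one. Keep later retests for the listings and for worst-value summaries.

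Align SAP 3.3.9 with the row: extend or explain the Visit 1 to 8 scope, and settle how a withdrawal visit can be an EOS assessment when Table 2 places EOS after ET.

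The cost is a small change to one derivation and a few lines of SAP text. No new data are needed, and the protocol's retesting practice is unchanged.

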8.3 Adverse Events

The definitions of an AE or SAE can be found in [Appendix 4](#).

Any AEs will be reported by the patient (or, when appropriate, by a caregiver, surrogate, or the patient's legally authorized representative).

The Investigator and any designees are responsible for detecting, documenting, and recording events that meet the definition of an AE or SAE and remain responsible for following up AEs that are serious, considered related to the study treatment or study procedures, or that caused the patient to discontinue study treatment or the study (see [Section 7.0](#)).

8.3.1 Time Period and Frequency for Collecting AE and SAE Information

All AEs and SAEs will be collected at the time points specified in the SoA ([Table 1](#)). Serious AE reporting will start at the time of consent. Any AE that occurs between the time of consent and prior to dosing on Day 1 will be recorded as medical history. All TEAEs will be collected following the first dose of study treatment on Day 1 through the Follow-up Visit (30 days after the last administration of study treatment).

All SAEs will be recorded and reported to the Sponsor/designee within 24 hours, as indicated in [Appendix 4](#). The Investigator will submit any updated SAE data to the Sponsor within 24 hours of it being available.

Investigators are not obligated to actively seek AEs or SAEs after conclusion of the study participation. However, if the Investigator learns of any SAE, including a death, at any time after a patient has been discharged from the study, and he/she considers the event to be reasonably related to the study treatment or study participation, the Investigator must promptly notify the Sponsor/designee.

The method of recording, evaluating, and assessing causality of AE and SAE and the procedures for completing and transmitting SAE reports are provided in [Appendix 4](#).

8.3.2 Method of Detecting AEs and SAEs

Care will be taken not to introduce bias when detecting AEs and/or SAEs. Open-ended and nonleading verbal questioning of the patient is the preferred method to inquire about AE occurrences.

8.3.3 Follow-up of AEs and SAEs

After the initial AE/SAE report, the Investigator is required to proactively follow each patient at subsequent visits/contacts. All SAEs and non-serious AEs of special interest (AESIs) (as defined in [Section 8.3.6](#)), will be followed until resolution, stabilization, the event is otherwise explained, or the patient is lost to follow-up up to database lock (as defined in [Section 7.5](#)). Further information on follow-up procedures is given in [Appendix 4](#).

8.3.4 Regulatory Reporting Requirements for SAEs

Prompt notification by the Investigator to the Sponsor/designee of an SAE is essential so that legal obligations and ethical responsibilities toward the safety of patients and the safety of a study treatment under clinical investigation are met.

The Sponsor and/or designee has a legal responsibility to notify both the local regulatory authority and other regulatory agencies about the safety of a study treatment under clinical investigation. The Sponsor and/or designee will comply with country-specific regulatory requirements relating to safety reporting to the regulatory authority, IRB, and Investigators.

Investigator safety reports must be prepared for suspected unexpected serious adverse reactions (SUSAR) according to local regulatory requirements and Sponsor policy and forwarded to Investigators as necessary.

An Investigator who receives an Investigator safety report describing an SAE or other specific safety information (eg, summary or listing of SAEs) from the Sponsor and/or designee will review and then file it along with the IB, and will also notify the IRB/IEC, if appropriate according to local requirements.

8.3.5 Pregnancy

All patients are required to meet the requirements relating to pregnancy and use of contraception described in the inclusion and exclusion criteria (see [Sections 5.1](#) and [5.2](#), respectively).

Serum pregnancy testing will be performed only for women of childbearing potential (WOCBP) at Screening (Day -28 to Day -1); the result must be negative for the patient to be eligible. A urine pregnancy test will be performed only for WOCBP on Day 1 (prior to dosing) and at every subsequent study visit through the follow-up visit (Visit 9). The serum pregnancy tests will be analyzed by the central laboratory, and the urine pregnancy tests will be analyzed locally.

- Details of pregnancies in female patients and, if indicated, female partners of male patients will be collected after the start of study treatment and until 30 days (ie, 1 menstrual cycle) after the last dose of study treatment.
- If a pregnancy is reported, the Investigator should inform the Sponsor/designee within 24 hours of learning of the pregnancy and should follow the procedures outlined in [Appendix 6](#).
- Abnormal pregnancy outcomes (eg, spontaneous abortion, fetal death, stillbirth, congenital anomalies, ectopic pregnancy) are considered SAEs.

8.3.6 Adverse Events of Special Interest

The following AEs will be classified as AESI in this study:

8.3.7 Disease-related Events and/or Disease-related Outcomes Not Qualifying as AEs or SAEs

Not applicable. Further information on general AE/SAE considerations is given in [Appendix 4](#).

8.4 Treatment of Overdose

For this study, any dose of >3 tablets of ATI-450/placebo per day OR 2 tablets of ATI-450/placebo taken at any single dosing time point (eg, morning dose, evening dose) will be considered an overdose. The dose of ATI-450 used in this study is based on doses previously studied in Phase 1, and plasma exposure is unlikely to exceed previously studied levels if patients adhere to dosing instructions. Given the blinded nature of the study, the above recommendations make the assumption that each blinded tablet contains 50 mg of ATI-450.

The Sponsor does not recommend specific treatment for an overdose.

In the event of suspected or confirmed overdose, the Investigator should:

- Undertake any supportive measures, as per Investigator judgment.
- Contact the Medical Monitor immediately.
- Closely monitor the patient for any AE/SAE and/or laboratory abnormalities until the risk is considered to be resolved as agreed with the Medical Monitor.
- Obtain a plasma sample for PK analysis and any other relevant interventions or assessments, if requested by the Medical Monitor (determined on a case-by-case basis).
- Document the quantity of the excess dose as well as the duration of the overdose in the eCRF.

Decisions regarding dose interruptions will be made by the Investigator in consultation with the Medical Monitor based on the clinical evaluation of the patient. Treatment of confirmed or suspected overdose with ATI-450 should consist of clinically appropriate supportive measures.

Any overdose associated with clinical symptoms will be recorded as an AE or SAE, as appropriate. Details of any signs or symptoms and their management should be recorded, including details of any treatments administered for the overdose. All overdoses with clinical symptoms meeting the SAE criteria must be reported as described in [Section 8.3.4](#).

8.5 Pharmacokinetics

Up to twelve (12) venous blood samples of approximately 2 mL each will be collected for measurement of plasma concentrations of ATI-450 and its primary circulating metabolite, CDD-2164, as specified in the SoA ([Table 1](#)). Instructions for the collection and handling of biological samples will be provided by the Sponsor/designee. The actual date and time (24-hour

clock time) of each sample will be recorded. The date and time of study treatment administration will also be recorded.

A PK sample will be collected if ECG withdrawal criteria are met, see [Section 7.1.1](#).

Samples will be used to evaluate the PK of ATI-450. Each plasma sample will be divided into 2 aliquots (1 each for primary analysis and back-up). Samples collected for analyses of ATI-450, CDD-2164 and other metabolite/enantiomer plasma concentrations may also be used to evaluate safety or efficacy aspects related to concerns arising during or after the study.

Genetic analyses will not be performed on these plasma samples. Patient confidentiality will be maintained.

At visits during which blood samples for the determination of PK of ATI-450 will be taken, 1 sample of sufficient volume can be used. Every effort will be taken to collect the blood samples as close as possible to the scheduled time points, but a window of ± 10 minutes is permitted for each blood draw. In instances where different assessments are due at the same time point, they will be performed such that the blood samples for PK analyses will be drawn at the correct time (as long as patient safety is not compromised).

Drug concentration information that may unblind the study will not be reported to study centers or blinded personnel until the study has been unblinded.

Any changes in the timing or addition of time points for any planned study assessments must be documented and approved by the relevant study team member and then archived in the trial master file and Investigator site file but will not constitute a protocol amendment. The IRB/IEC will be informed of any safety issues that require alteration of the safety monitoring scheme or amendment of the ICF.

If a patient refuses blood collection for PK analysis, this will not be considered a protocol violation as the PK analysis is a secondary objective.

Details regarding the processing and shipment of all blood samples can be found in the Laboratory Manual.

8.6 [REDACTED]

[REDACTED]

[REDACTED]

